6.2.4 Treatment Visits

In accordance with the Schedule of Evaluations (section 6.1 above), treatment-related measures will be collected in months 3 and 5 as follows:

- Hamilton: The Hamilton Rating Scale for Depression (HRSD)⁵⁶ (as a validated objective, interview-based assessment of depression). Atypical depression symptoms as part of the Structured Interview Guide for the Hamilton Depression Rating Scale, Seasonal Affective Disorders version (SIGH-SAD)⁶⁰ (as atypical symptoms in particular respond to light treatment⁶¹) Mania⁶² ratings (to document any clinical induction of manic symptoms by the wake or light interventions) – on ovulation night (LSH), daily on LHS+1 – LHS+2 (during intervention) and once after light treatment on LHS+8-9 (post-intervention assessment).
- Beck Depression Inventory (BDI)⁵⁷ (as a validated subjective assessment of depression) – on ovulation night (LSH), daily on LHS+1 – LHS+2 (during intervention) and once after light treatment on LHS+8-9 (post-intervention assessment),
- Beck Anxiety Inventory (BAI)⁵⁸ (as many women with PMDD report anxiety symptoms)⁶³ – on ovulation night (LSH), daily on LHS+1 – LHS+2 (during intervention) and once after light treatment on LHS+8-9 (post-intervention assessment),
- The Psychological General Well-Being Index (PGWI)⁶⁴ – on ovulation night (LSH), daily on LHS+1 – LHS+2 (during intervention) and once after light treatment on LHS+8-9 (post-intervention assessment),

- Daily mood self-ratings (DMR)⁵⁴ that include core PMDD symptoms of anxiety and irritability – collected daily on LHS+0 through LHS+2 (for wake therapy effects) and daily LHS+3 through LHS+10 (for light treatment effects),
- Pittsburgh Sleep Quality Index (PSQI)⁶⁷ to assess subjective sleep quality – once on LHS+8-9 (post-intervention assessment),
- Visual analogue scale⁶⁸ to assess subjective sleep quality – once on LHS+8-9 (post-intervention assessment),
- Ovulation testing performed for 7 days starting on menstrual cycle day 10 in months 3 and 5 to determine luteinizing hormone surge (LHS). Participants will contact Study Coordinator with their time of first menses (cycle day 1) to determine cycle day 10 and schedule appointment for collecting study forms and equipment,
- Actigraphy will be collected for 10 days starting the day of LHS to monitor baseline sleep, light and activity measures at home,
- Urine collection for 30 hrs performed between days 8-9 after LHS.

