9.2 Sample Size and Randomization

For our primary outcome measures of mood, based on our earlier data reflecting

seven days of light exposure alone² (i.e., without the ‘priming’ effect of wake therapy), we predict the following changes in mood in PMDD subjects (N = 40) after Late Wake Therapy plus AM Light vs. Early Wake Therapy plus PM Light: A significantly greater improvement (decrease in raw score) will be detected at the p = .05 level with (a) 71% power in Hamilton Rating Scale for Depression (HRSD) Score (Mean difference 3.15±9; effect size = .324); (b) > 99% power in atypical score (Mean difference 4.45±5; effect size = .78); (c) > 99 % power in Structured Interview Guide for the Hamilton Depression Rating Scale, Seasonal Affective Disorders (SIGH-SAD) Items (Mean difference 7.0±11; effect size = .627); (d) 86% power in Beck Depression Inventory (BDI) score (Mean difference 6.30±15; effect size = .378).

For the recovery criterion of $\geq 50\%$ decrease from baseline (Chi Square analyses): (a) 97% power for HRSD score (difference in proportions: .44); (b) 70% power for atypical score (difference in proportions: .30); (c) 86% for SIGH-SAD score (difference in proportions: .325); and (d) 93% power for BDI score (difference in proportions: .40). For the remission criterion of reduction to a score of ≤ 8 (Chi Square analyses): (a) 89% power for the SIGH-SAD score; (b) 44% power for the BDI score. All tests are two-tailed.

We also performed power analyses for the primary hypotheses, incorporating the longitudinal nature of the design for the proposed Random Regression model (also known as Multilevel Models, or Growth Curve Models). Procedures describes by Hedeker et al.⁶⁹ for Random Regression Models, with the above data, was used for the proposed study to estimated needed sample size. We assume a Type-I error level (alpha-level) of 0.05, drop-out rate of 10% to 15% and an autoregressive covariance structure, with correlation between sequential assessments set at 0.45 (based on our previous data). We are confident based on our results from these two separate approaches that the proposed study will have minimum power of 80% to yield a statistically significant result for a medium effect size. Here, medium effect size is defined as a treatment difference increasing linearly from 0 at baseline to .5 SD units at the last time point. Type 1 error will be controlled by correcting the p-value per domain.

Treatment Assignment Procedures

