Specifically, data for hypothesis 1.A. will be analyzed using a Random Regression Model (RRM), a generalized linear model described by Gibbons et al.,⁷⁴ Hedeker et al.⁶⁹ and Laird.⁷⁵ The random effects method has several advantages over more traditional analytic approaches such as a change score, end-point or repeated measures analysis of variance. This method allows the inclusion of subjects with missing data or those who were terminated early in the study, without relying on data imputation procedures. This method provides an estimate of the individual variability around the population trend, the variability of the individual intercepts (baseline values) and slopes (changes across time), and the correlation between them. A fully saturated treatment by time model will be utilized for inference. Co-variance structure will be chosen based on Akaike's Information Criterion (AIC). Random treatment effects also will be evaluated for importance based on the model AIC. This plan allows for any group level effects to be incorporated into the model. Denominator degrees of freedom will be calculated using the Kenward-Roger small sample correction. All subjects will be included in the analyses, and we will not focus only on subjects who complete the study. Our methods for data analyses include all subjects with any valid data points in the analyses. Secondary analyses will be performed on data from completers. Type 1 error will be controlled by correcting the p-value per domain. For hypothesis 1.B, an individual's slope for each of the dependent variables listed above will be calculated and will be used for correlational analysis using the Pearson method. In addition, we will examine the number of responders. The operational definition of the criteria for

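### The random-regression power in 9.2 describes a linear trend, but the saturated model in 9.6 has no trend parameter and no contrast is named to decide H1.A

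*Combined protocol and SAP*

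**What the plan says.** Section 9.2 gives a second power calculation, for the random regression model. Its assumptions are: "We assume a Type-I error level (alpha-level) of 0.05, drop-out rate of 10% to 15% and an autoregressive covariance structure". Neighbouring ratings are taken to correlate at .45, a value drawn from the investigators' earlier data. The conclusion is that "the proposed study will have minimum power of 80% to yield a statistically significant result for a medium effect size", where "medium effect size is defined as a treatment difference increasing linearly from 0 at baseline to .5 SD units at the last time point". The number of assessments, the correlation between a woman's two treatment cycles, and the test or its degrees of freedom are not given.

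Section 9.6 (General Approach to Data Handling and Statistical Analyses) then says: "A fully saturated treatment by time model will be utilized for inference". It specifies Kenward-Roger denominator degrees of freedom and selection of the covariance by AIC. It names no contrast, F-test or numerator df.

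Section 6.2.4 schedules the HRSD, BDI, BAI and PGWI in each treatment month on the night of the LH surge, then "daily on LHS+1 – LHS+2 (during intervention) and once after light treatment on LHS+8-9 (post-intervention assessment". That makes four ratings per treatment. H1.A (section 9.1) concerns the change from baseline to post-intervention, and section 9.5.1 sets baseline at month 2.

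**The concern.** A linear trend spends one degree of freedom on the effect shape assumed in 9.2. A saturated model estimates a separate treatment difference at every rating. The test most software reports from such a model, the treatment-by-time F-test, spreads the same signal over several degrees of freedom. The effect that was powered is therefore not a parameter of the model named for inference.

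Two things are at stake.

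- **Power.** A true .5 SD benefit at the end of treatment is more likely to be missed than 9.2 suggests if the multi-df test decides.
- **Interpretation.** A multi-df test can be significant because of a passing difference at LHS+1 or LHS+2, right after wake therapy. That would not support H1.A.

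Because the text fits several tests with quite different power, the choice could also be made after the data are seen.

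**Working it through.** **Inputs from the documents.** N = 40 (9.2), each woman receiving both treatments. Drop-out is 10-15%, so 34 to 36 women (40 × .85 = 34; 40 × .90 = 36). Two-sided alpha is .05. Correlation between sequential assessments is ρ = .45. The final difference is .5 SD. There are four ratings per treatment (6.2.4).

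**Assumptions, because 9.2 is silent.** Four assessments enter the model. The correlation between the two cycles is r. The treatment differences then have covariance 2(1−r)·R/n, with R autoregressive. Denominator df are n−1. The difference d is linear either by visit, (0, .167, .333, .5), or by day, (0, .059, .118, .5), taking the last rating at day 8.5.

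**Formulas.** Let m = n / [2(1−r)].

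- A = d′R⁻¹d = Σ(d_k − ρd_{k−1})² / (1−ρ²), summed over visits 2 to 4, since the first difference is 0.
- B = A − (1′R⁻¹d)² / (1′R⁻¹1). This is the part of A left once the LHS difference is free.
- Noncentrality is m·A for the zero-start trend (1 df), for the joint test of treatment at all four visits (4 df), and for the test of the three later visits with the LHS difference fixed at 0 (3 df).
- Noncentrality is m·B for the ordinary interaction (3 df, LHS difference free).
- Noncentrality is m·(.5)² for the single contrast at LHS+8-9.
- Power is the upper tail of the noncentral F beyond its .05 critical value.

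**Numbers by visit.** A = (.1667² + .2583² + .35²)/.7975 = .2170/.7975 = .2721. 1′R⁻¹d = .55 × .775/.7975 = .5345. 1′R⁻¹1 = 1 + 3 × .3025/.7975 = 2.138. B = .2721 − .2857/2.138 = .1385.

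**Numbers by day.** A = .2654 and B = .1861.

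**The plan's own figure first.** 80% cannot be derived from the stated inputs alone, because r and the number of assessments are missing. With r = .45 and n = 34, m = 34/1.1 = 30.91. The trend noncentrality is 8.41 (by visit) or 8.20 (by day), and power is 80% or 79%. This setting is a calibration that comes close to the claim; the documents do not state it.

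**Other tests on those same inputs (n = 34, r = .45):**

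| Test | df | Noncentrality (visit / day) | Power (visit / day) |
|---|---|---|---|
| Linear trend, zero start | 1 | 8.41 / 8.20 | 80% / 79% |
| Treatment-by-time, LHS difference free | 3 | 4.28 / 5.75 | 34% / 45% |
| Joint test at all four visits | 4 | 8.41 / 8.20 | 56% / 55% |
| Later visits, LHS difference fixed at 0 | 3 | 8.41 / 8.20 | 62% / 61% |
| Single contrast at LHS+8-9 | 1 | 7.73 | 77% |

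Relative to the trend, the multi-df tests lose about 18 to 46 percentage points and the single contrast loses 2 to 3.

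**Sensitivity to the unstated inputs (same formulas):**

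| n, r | m | Trend, zero start | 3-df, LHS free | 4-df | 3-df, LHS at 0 | LHS+8-9 contrast |
|---|---|---|---|---|---|---|
| 34, 0 | 17.0 | 54-55% | 20-26% | 31-32% | 36-37% | 52% |
| 40, .45 | 36.4 | 86-87% | 40-53% | 64-65% | 70-71% | 84% |
| 34, .7 | 56.7 | 96-97% | 59-73% | 84-85% | 88-89% | 95% |

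The level moves a great deal with r; the ordering does not. In every row each multi-df test is below the trend, and the LHS+8-9 contrast is above each multi-df test.

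**The case against.** The strongest reply is that 9.6 commits to a model and not to an omnibus test. A saturated model allows a 1-df contrast, and H1.A already points to one, since the change from baseline to post-intervention reduces to the treatment difference at the last rating once month 2 is the common baseline. Equally, 9.2 defines an effect shape and never says that the 80% belongs to a 1-df test. Section 9.6 also speaks of individual slopes. All of this stands. The mismatch is therefore one of specification: those slopes describe individual variation, and no sentence turns H1.A into a named test.

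A reader might infer that the trial has only about 20-30% power and would miss a true benefit in most trials of this size. The documents do not support that. Such values arise with a free LHS difference and little or no between-cycle correlation. In that setting (n = 34, r = 0) a trend with the LHS difference also left free has only 32-41%, so setting the low figure against 80% mixes a free and a fixed starting difference. The plan's baseline is shared by both treatments, and 9.2 starts the difference at 0, which argues against the free-start version. Nor is there a low ceiling on multi-df power: at r = .7 and N = 40 (m = 66.7) the 4-df test reaches 91%.

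**Conclusion.** The point holds as a gap between the power statement and the inferential model. The effect powered in 9.2 is not a parameter of the mean model in 9.6, and the test of H1.A is left open. If a multi-df treatment-by-time test decides, its power is below that of the trend.

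Under the calibrated assumptions the figures are 34-45%, 55-56% or 61-62%, depending on which multi-df test is run, against about 80% for the trend and 77% for the LHS+8-9 contrast. These values rest on four assessments, a between-cycle correlation of .45, n = 34 and a linear true effect. They are conditional illustrations and not the plan's actual power, which cannot be fixed without the missing inputs. The per-domain p-value correction in 9.6 is not reflected in the .05 used here and would lower every figure.

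**What to change.** In 9.6, keep the saturated mean model and add that H1.A is tested by one pre-specified 1-df contrast: LWT+AM BWL minus EWT+PM BWL at the post-intervention rating (LHS+8-9), with month 2 as the shared baseline. State that the overall treatment-by-time F-test is descriptive. The Figure 1 legend places this rating at LHS+7/8, so the label should be made the same in both places.

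In 9.2, restate the random-regression power for that contrast, giving the number of assessments and the between-cycle correlation assumed.

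The cost is two sentences in 9.6 and one recalculated figure in 9.2, with no new patients or data. Differences confined to LHS+1 and LHS+2 become secondary, and the stated power may come out slightly lower.

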This design allows us to complete the studies at least two days before the next expected menstrual period. Measuring the circadian profile of urinary melatonin over 2 nights for 30+ h will allow us to assess phase, duration and amplitude changes of melatonin reflective of the underlying circadian pacemaker. In addition, we will assess phase-shift responses of melatonin to light in relation to other critical biological rhythm measures of sleep and activity. To document the sleep/wake cycle and exposure to light intensity and spectra, we will use the Actiwatch device (see description below).

[figure not shown]

Figure 1. Study flow: The luteinizing hormone surge (LHS) documents ovulation, c. menstrual cycle day (CD) 14. Urine samples for 6-sulphatoxy-melatonin (6-SMT) and reproductive hormones (RHs) will be collected for 30+ hours over 2 nights between days 8-9 after the LH surge (c. CD 22-23) in months 2,3,5; actigraphy will begin the day of LHS and continue until day 10 after the LHS (CD 14-24) of months 2,3,5; late wake therapy (LWT) or early wake therapy (EWT) will be administered at home on the night of the LHS; bright morning (AM) or evening (PM) light will be administered on days 1-7 after the LHS (CD 15-21) in a counterbalanced, cross-over design in months 3 and 5. Mood ratings (HRSD+BDI) will be collected as follows: Months 1 & 2 – once per week; Months 3 & 5 – LHS + 0 (Pre-

LWT/EWT), daily LHS +1 → LHS + 2 and once the evening after last treatment (LHS +7/8). Visual Analogue Scales (VAS) for depressed mood, anxiety, affective lability, irritability (Daily Mood Ratings)(core PMDD symptoms) collected daily during Months 1 & 2, and twice daily on LHS + 0 through LHS + 2 (for wake therapy effects) and daily LHS + 3 through LH + 10 (for light treatment effects) in Months 3 & 5. HRSD will be collected once during Month 4 and a once a month after Intervention 2 to monitor relapse.

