9.5 Outcomes

9.5.1 Primary Outcome

- Treatment-Related Mood Rating Changes from Baseline (month 2) to post intervention (months 3,5) :
Mood ratings include Hamilton Rating Scale for Depression (HRSD), Beck Depression Inventory (BDI), atypical depression symptoms as part of the Structured Interview Guide for the Hamilton Depression Rating Scale, Seasonal Affective Disorders version (SIGH-SAD), Beck Anxiety Inventory (BAI), mania ratings, the Psychological General Well-Being Index (PGWI) and daily mood self-ratings (DMR) that include core PMDD symptoms of anxiety and irritability as required during diagnostic evaluation, before, during and after each wake and light intervention at the same time of day (between 15:00-17:00 h). To assess more acute effects on mood that may occur more rapidly during the wake interventions, subjects will complete DMRs twice daily beginning the evening before the wake therapy intervention and continuing until the morning after the recovery night of sleep.
- Treatment-Related Urinary 6-sulfatoxymelatonin (6-SMT) Changes from Baseline (month 2) to post intervention (months 3,5) :
6-SMT is a principal melatonin metabolite that is abundant in urine, well correlated with plasma melatonin, and serves as an excellent marker for circadian phase response.
- Treatment-related changes in objective and subjective sleep measures:
Using actigraphy, we will obtain objective measures of the sleep/wake cycle to ensure appropriate sleep/wake times during wake therapy, and during the light interventions as it is an important biological rhythm with which to compare the intervention-induced melatonin rhythm changes. To assess subjective sleep quality, we will use the Pittsburgh Sleep Quality Index (PSQI) and a visual analogue scale.

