Actiwatches: Activity and illumination will be examined to determine time-in-bed and any naps that occur during the day. Daily total sleep time, wake time, number of awakenings and distribution of lengths of awakenings for night and day separately in each 24 h period will be determined using the automated sleep-wake scoring algorithm and custom SAS procedures that we have developed.⁷⁰ Extended cosinor analyses⁷⁰ will be done to determine the mesor, amplitude and acrophase of activity and illumination and the f-statistic (with higher values representing more robust and synchronized rhythms that we expect to correlate with improved mood). The mean and maximum light intensities (in lux) and the number of minutes above 1,000 lux

also will be examined. Analyses then will be done comparing activity, sleep and light exposure between groups and time of light intervention with the light and activity summary variables as continuous covariates. Baseline pre-intervention values and post-intervention activity and illumination values also can be compared for a specific light pulse. These analyses will determine if the following variables predict the magnitude of treatment and phase-shift responses: 1) The timing of activity onset and offset, 2) The amplitude of activity at baseline, 3) The illumination levels at baseline.¹ For young adults, the Actiwatch is an accurate method for recording both the in-bed interval and for estimating the time asleep.⁷¹ Although presumably less accurate on a nightly basis than PSG, the Actiwatch is capable of several weeks of round-the clock recording, which would not be feasible with PSG either in the CTRI or at home.

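### The mood model in section 9.6 makes no use of the pre-treatment LHS+0 rating as a baseline for each treatment month, and leaves open which treatment contrast is tested

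*Combined protocol and SAP*

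**What the plan says.** - **Model.** Section 9.6 analyses hypothesis 1.A with a random regression model: "A fully saturated treatment by time model will be utilized for inference". Baseline enters as part of the response, through "the variability of the individual intercepts (baseline values) and slopes (changes across time), and the correlation between them". Covariates are named only for the actigraphy analyses ("with the light and activity summary variables as continuous covariates"), not for mood.
- **Ratings.** Section 6.2.4 schedules HRSD/SIGH-SAD, BDI, BAI and PGWI in each treatment month "on ovulation night (LSH), daily on LHS+1 – LHS+2 (during intervention) and once after light treatment on LHS+8-9 (post-intervention assessment". The Figure 1 legend in section 3 confirms, for HRSD and BDI, that the first of these precedes wake therapy.
- **Baseline.** Section 9.5.1 defines the primary mood outcome as "Treatment-Related Mood Rating Changes from Baseline (month 2) to post intervention (months 3,5").
- **Power.** Section 9.2 claims at least 80% for the random regression model, where "medium effect size is defined as a treatment difference increasing linearly from 0 at baseline to .5 SD units at the last time point". It assumes alpha 0.05, 10% to 15% dropout and an autoregressive correlation of 0.45.
- **Not stated.** The plan does not say which visits are levels of time in the model, whether inference rests on the interaction or on the last-visit difference, how LHS+0 and the last rating correlate, or how variable LHS+0 is.

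**The concern.** In a cross-over, the useful baseline for the treatment comparison is one that differs between a woman's two treatment months. Month 2 gives one value per woman. It drops out of her AM-minus-PM difference and cannot reduce the variance of that difference. LHS+0 gives one value per treatment month and could reduce it, but the plan gives it no such role.

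A saturated treatment-by-time model that includes LHS+0 as a time level gives each treatment its own free mean there. The treatment-by-time contrast at the last rating is then a difference of changes from LHS+0. It carries the full noise of two pre-treatment ratings, and a chance LHS+0 difference between a woman's two months passes straight into the estimated effect. The power statement assumes no treatment difference at baseline, but the analysis model does not use that information. With 40 women, avoidable variance in the primary contrast matters.

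**Working it through.** **The plan's own figure.** The 80% cannot be firmly reproduced, because the number of time points and the SD behind the 0.5 are not given. One reading comes close: 34 to 36 evaluable women (40 less 15% or 10%), 0.5 SD of the within-woman difference, baseline and last rating correlated 0.45, free baseline. Then the variance is 2(1 - 0.45) = 1.10, and the normal approximation gives 79.4% to 81.6%. With AR(1) over the four scheduled ratings, r = 0.45³ = 0.091 and the same test gives 58.0% to 60.5%.

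**Set-up.** Let D0 and D1 be a woman's AM-minus-PM differences at LHS+0 and LHS+8-9, with correlation r. Take the variance of a single rating as 1 and her two months as independent, so D0 and D1 each have variance 2.

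- Change contrast, D1 - D0: 2 + 2 - 4r = 4(1 - r)
- Post-treatment difference, D1 alone: 2
- D1 adjusted for D0, or LHS+0 means constrained equal: 2(1 - r²)
- Ratio of adjusted to change: (1 + r)/2, below 1 for any r < 1

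**Power.** N = 40, difference 0.5, two-sided 0.05 with no per-domain correction, noncentral t with noncentrality 0.5/√(V/40):

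| r | Contrast | V | SE | Noncentrality | Power |
|---|---|---|---|---|---|
| 0.45 | change | 2.200 | 0.2345 | 2.13 | 55% |
| 0.45 | post only | 2.000 | 0.2236 | 2.24 | 59% |
| 0.45 | adjusted | 1.595 | 0.1997 | 2.50 | 68% |
| 0.091 | change | 3.636 | 0.3015 | 1.66 | 37% |
| 0.091 | post only | 2.000 | 0.2236 | 2.24 | 58.7% |
| 0.091 | adjusted | 1.983 | 0.2227 | 2.25 | 59.0% |

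**Smaller spread at LHS+0.** If its SD is k times that at LHS+8-9, the change variance becomes 2(1 + k² - 2rk). The adjusted variance is unaffected.

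- r = 0.45, k = 0.75: V = 2(1 + 0.5625 - 0.675) = 1.775, power 64%, so adjustment gains about 5 points.
- r = 0.45, k = 0.5: V = 2(1 + 0.25 - 0.45) = 1.600, power 68%, so no gain.
- r = 0.091: gains of 14 points at k = 0.75 and 6 points at k = 0.5.

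**Other SD definition.** With 0.5 in SDs of the within-woman difference and 34 to 36 evaluable (normal approximation):

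- r = 0.45: change 79.4-81.6%, post only 83.0-85.1%, adjusted 90.4-91.9%.
- r = 0.091: change 58.0-60.5%, post only 83.0-85.1%, adjusted 83.3-85.4%.

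A simulation of 20,000 runs at n = 36 with a period term gave 79.2% (change) against 89.5% (adjusted) at r = 0.45, and 58.0% against 82.6% at r = 0.091.

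**The case against.** The strongest reply is that section 9.6 never makes LHS+0 a time level and never names the interaction as the test. The primary outcome is anchored on Month 2, and 9.6 presents its method as an improvement on a change score. If Month 2 is the baseline, it cancels, nothing noisy is subtracted, and the treatment comparison is the post-treatment difference. A saturated model can also be tested at its last visit. This stands, and on either route the gain is only the 0 to 10 points shown. There is evidence the other way: 9.5.1 covers ratings before, during and after each intervention, and 10.3.3 judges improvement by before-and-after differences. The text does not settle it.

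Three stronger conclusions are tempting, and the documents do not support them.

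- **That the plan loses 22 points of power that the baseline would restore.** The drop from 59% to 37% requires a change contrast that 9.6 does not specify, together with r = 0.09, equal variances and independent months. At that r, the baseline itself adds 0.3 points over the post-only test. The rest comes from not subtracting noise.
- **That the stated 80% is refuted.** With a correlation of 0.45 between a woman's two months, the change variance at r = 0.45 is 2(1 - 0.45) × 2(1 - 0.45) = 1.21. A free-baseline test with 40 pairs then has 80% power.
- **That the power model's zero baseline difference commits the analysis to a constraint.** It describes the assumed shape of the effect.

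The equal-variance assumption is also open to doubt. LHS+0 falls near cycle day 14, and entry requires a mean follicular HRSD of at most 7 against at least 14 premenstrually, so mid-cycle scores may be low and less spread.

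Finally, the Month 5 LHS+0 rating follows the first treatment, so adjusting for it or constraining it relies on no carry-over. That is a real condition, but the plan already anticipates minimal carry-over and provides a washout month.

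**Conclusion.** The point holds as a gap in specification with an efficiency cost of uncertain size. The plan collects a baseline specific to each treatment month and does not use it to adjust the treatment comparison. The baseline it names cannot do that job.

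If the tested contrast subtracts LHS+0, adjustment raises power from 55% to 68% at r = 0.45 and from 37% to 59% at r = 0.09, under the stated assumptions. The gain is smaller, and can vanish, if LHS+0 is less variable than the last rating. If the post-treatment difference is tested, adjustment adds 7 to 10 points at r = 0.45 and about 0 at r = 0.09. Apart from one degree of freedom, the adjusted contrast is never less precise than either alternative, whatever r and the LHS+0 SD turn out to be. That makes it worth fixing in advance although no single loss of power is established.

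**What to change.** In section 9.6, for HRSD, SIGH-SAD, BDI, BAI and PGWI:

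1. List the visits that are levels of time in the model.
2. Name each month's LHS+0 rating as the baseline for that treatment period.
3. Either constrain the treatment means to be equal at LHS+0 and leave the treatment-by-time terms free afterwards, or adjust the within-woman post-treatment difference for the within-woman LHS+0 difference.
4. Name the adjusted LHS+8-9 treatment difference as the primary contrast. The Figure 1 legend gives LHS+7/8 for this rating and should be reconciled with section 6.2.4.
5. Keep Month 2 for describing change from the untreated cycle. The outcome definition in 9.5.1 can stay, since Month 2 cancels from the treatment comparison.

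The cost is SAP wording and one constraint or covariate, with no new data and no added burden. The price is one degree of freedom and explicit reliance on no carry-over into the Month 5 LHS+0 rating.
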